Version #14 7/12/21

Official title: Mealtime Partnerships for People With Dementia in Respite Centers and at Home

NCT03622814

Document date: 10/12/2023

Principal Investigator:

[name], RN
MUSC College of Nursing

A. Introduction/Hypothesis

Two of the most challenging conditions that negatively affect persons with dementia (PWD) living in the community are: (1) weight loss leading to frailty, and (2) social isolation leading to diminished quality of life (QOL). Lack of caregiver (CG) skills related to meals, dysfunctional CG and PWD behaviors during meals, and diminished PWD social skills leading to isolation are well-documented factors influencing nutritional outcomes. This study will test the efficacy of an intervention that empowers CGs and volunteers or staff in respite care centers (RCCs) who interact with PWD during mealtime. Specifically, a train-the-trainer program, **Partners at Meals (PaM)** derived from the theoretically-based **C3P Model of Changing the Place** (home or RCC), **Changing the People** (CG or volunteer) and **Changing the Person** (PWD) will be used to improve nutritional outcomes and QOL. Family members are the primary CGs of community dwelling PWD. We **hypothesize** our intervention will: (1) improve quality of life by better equipping family caregivers and respite care providers to manage a chronic illness with significant burden (Alzheimer's disease and related dementias), (2) improve palliative care for this terminal illness while some change is feasible, and (3) enhance innovation in a community-based practice (Respite Care Centers). As such, the products of this study are of high significance.

Family-managed care is critical in promoting quality of life (QOL) and health in Alzheimer's disease and other dementias. The Partners at Meals (PaM) intervention emphasizes focusing on more than just "changing" a PWD, but also intervening with the People with whom they interact and Place where meals occur. With this intervention, CGs and volunteers or staff at RCCs partner and modify mealtime at a point when the PWD is still able to express preferences and engage in the meal process, and develop a PWD-centered plan of mealtime care. Of note, our pilot work indicated that CG's report of mealtime behavior may be inaccurate because CG and other family members may overlook key cues/triggers to dysfunctional behavior. Thus, to **improve this identification process, a secure and HIPAA-compliant telehealth component (Doxyme)** is used to record dysfunctional behaviors displayed by the PWD on a 'tablet'. The CG interacts with their "partner" volunteer, the RCC staff or MUSC Interventionst (AIM 4) either through a real-time connection or sharing of the recorded file so that together, they can problem-solve issues and modify the plan of care. This CG-volunteer/ staff member partnership also fosters consistency across settings (AIMS 1-3), as well as imparts skills and self-efficacy for care management for both parties, improves QOL for the CG and the PWD, improves mealtime outcomes for the PWD, and promotes better health outcomes.

Research design. A randomized cluster-design trial will be conducted in two large RCCs with six sites that serve primarily white and African American PWDs. RCCs will be randomized to the **intervention condition (Partners at Meals; 2 sites)** or [**'enhanced usual care' (EUC)**] (4 sites). The primary unit of analysis is the PWD and CG: 60 PWDs, 60 CGs will be enrolled; it is estimated that up to 60 volunteers/staff/managers may be enrolled. The CG and RCC volunteer or staff member is another dyad for analysis, as is the RCC volunteer/staff member and the PWD. Additionally, RCC Managers at both PaM and EUC sites will be interviewed regarding barriers to implementation, ways to enhance the project, and possible causes of discharge of PWD from the study related to nutritional problems.

Additionally, to explore the feasibility of program replication and widespread adoption, an online

global survey of Respite Care Providers and their respective agencies will be conducted on the use of telehealth/videoconferencing technologies to deliver individualized educational support services to families in-the-home.

Partners at Meals (experimental condition) uses the C3P Model to direct change in three key areas (place, person, PWD) whether at the RCC or in the home. In the intervention sites, project staff will train the RCC volunteers or staff members, who will train CGs to more effectively manage meals based on assessment at the Center, and will subsequently use the telehealth solution in the home. Tailoring the plan to the home is critical to family-managed sustainability. The intervention will be delivered through each CG-volunteer /staff member dyad, and each PWD-CG dyad will be enrolled for 6 months. CGs and staff/volunteers in the EUC condition will have training focused on CG needs alone for support from family and others to manage care. A comprehensive process evaluation plan will be used to monitor implementation and foster dissemination.

Specific Aims:

Aim 1: To use a repeated-measures, randomized control design to assess the relative efficacy of Partners at Meals (PaM) vs. enhanced usual condition (EUC) in terms of the following PWD outcomes at baseline, and one-month intervals: nutritional status (weight, photography of pre- and post-food consumed); dysfunctional behaviors at meals (Edinburgh Feeding in Dementia scale XL with additional fields and questions added); quality of life (QOL-AD)

Main hypothesis: Participation in PaM will be associated with improved weight maintenance and decreased dysfunctional mealtime behaviors (the latter of which is the presumed mechanism of change).

Aim 2: To assess the relative efficacy of the Intervention vs. EUC in terms of the following. CG: quality of life (Euro-QOL), burden (Zarit Burden Scale), depression (CES-D), and self-efficacy for managing meals at home; b) RCC volunteer or staff: self-efficacy for training and management of mealtime issues; c) RCC director/manager: satisfaction with the program and willingness to maintain the program post-funding.

Aim 3: Conduct a process evaluation and content analysis to assure adherence, feasibility (e.g. using the telehealth tablet at home), reach, and maintenance to inform dissemination and adoption.

Exploratory Aim 4: To assess efficacy and outcomes of PaM when research staff implements the Intervention.

B. Significance and Innovation:

This trial examines patient-centered (PWD) outcomes when changes occur in behavior and in the environment. We lay the groundwork to examine the effectiveness and sustainability of a train-the-trainer program that could be disseminated and adopted by national organizations and community agencies through various media to manage mealtimes for this vulnerable population. With the demographic changes and resulting CG burden, comes the need for changes in the way health services are delivered. Tailored and dynamic plans that manage meals need to be developed, and care needs to be delivered in the community, where older people prefer to live and where resources are accessible and tailored to the culture and context. Along these lines, the PaM intervention focuses on two community sites – the home where meals are delivered by the CG, and the RCC where volunteers and staff assist with meals. Our implementation model uses

the train-the-trainer approach (train volunteers or staff to then train CGs) to deliver an intervention posited to change QOL issues for both the CG and the PWD, as well changing nutrition-related outcomes in the PWD. Several major nutritional enhancement initiatives to date have focused on CGs or PWDs but not both, as does the PaM program. There have been some successes among community-based programs that improved CGs health parameters and their ability to handle behavioral issues. However, studies are needed that describe capacity-building community interventions for the CG that influence PWD health parameters beyond QOL, which is notably influenced by CG health. Although our intervention is targeted to Respite centers, it could be easily extended to Adult Day Centers (medical model) that provide respite services to families. The impact of the proposed study is translational as it effectively builds upon the foundational NIH supported studies (REACH, Savvy Caregiver, NYUCI) one of which, the Savvy Caregiver, has been translated into a ‘transportable version’, something we feel we are close to achieving in this efficacy study and will use a component of in our ‘enhanced usual care’ group. Furthermore, this study addresses an unexplored important area – patient-centered outcomes related to a dyadic interaction - impact on PWD health. The focus to date on CGs outcomes implicitly assumes that change in that domain will yield positive results for ‘patients’. If PWD health benefits are demonstrated, this may lead to a potential policy implications related to CG support.

Innovations proposed by this study are five: a potential to change how and where services in dementia caregiving are delivered; potential to demonstrate a novel Train-the-Trainer model using volunteers or staff-CG dyads supported by a tele-health intervention; a focus on multiple dyads (i.e., PWD-CG, CG-volunteers or staff, volunteers or staff -PWD); the use of technology to enhance management of a disease that often leaves CGs isolated and unsupported; and a development of a low-cost sustainable intervention.

C. Rationale and Approach:

Study Overview:

Collaborating with the 2 respite care organizations and up to 180 subjects, a cluster design will be used to determine the efficacy of the Partners at Meals (PaM) train-the-trainer program compared to enhanced usual care (EUC). Two groupings of sites will be created in attempt to balance size and racial distribution: the largest site, which is racially diverse (The ARK), will be paired with a site (in the Respite Care Charleston system), which is not diverse: Together they will be one Site for treatment condition and analysis. The other four sites in the Respite Care Charleston system that together have approximately the same diversity and size, will be joined to create a second Site. These two Sites will then be randomized to PaM and EUC. All subjects (PWD, CG and RCC volunteers) will be followed for 6 months or until discharge or voluntary termination. The biostatistician will determine the cluster randomization. An ongoing process, impact and outcome monitoring plan is planned.

We will conduct an ‘enhanced usual condition’ training to identify ways that CGs communicate with family and friends to delegate challenging aspects of caregiving. Inspired by a unit of the Savvy Caregiver, the EUC will include a 30-minute presentation at sites with a follow-up 30-minute role-play regarding identifying challenging issues, ways of communication and ways to share those elements of caregiving that could be accomplished by others. When the site ‘comes on board’, the Program Manager will deliver the training and repeated every 6

months while the project is in progress for new CGs. Additionally, the staff of the EUC sites will be included in the teaching, and will facilitate discussion with the CGs during the interim. The program staff will attend the EUC site's support group every two months (or more frequently if needed) to see if CGs need guidance and discuss issues with the EUC staff.

Further, every attempt will be made to include PWDs with similar levels of cognitive/behavioral disabilities in both the PaM and EUC conditions; however, since this is cluster design, we cannot assure an equal balance.

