Administrators/Managers at the respite sites **will be interviewed** by the Program Manager every 3 months that the study is in place for satisfaction, willingness to continue the program after completion, any CG or volunteer dissatisfaction, and are asked for data regarding discharge or hospitalization of study participants to determine if the cause could be related to nutrition-related changes. The Administrator/Manager and the project staff will ‘check-in’ every month, or more often if needed, to report any urgent problems or issues that need a timely resolution. However, the Administrators/Managers will not be consented as they are not research subjects but engaged in research (Offsite form attached) and we will be collecting feasibility and evaluation/satisfaction information from them. **Formal evaluation** of the Volunteer or RCC Staff, CG and PWD will occur at baseline, monthly and at the end of enrollment (6 months) or earlier if the CG or PWD withdraw or are withdrawn (see next section).

If requested, a step-by-step outline of the sessions used to train the Volunteer or RCC Staff, and then the CG by the Volunteer or-RCC Staff as well as ‘booster’ sessions can be provided to the IRB, as well as weekly and monthly review activities accomplished by research team members.

Measures, data sources and collection. As noted in the Aims, there are key outcome measures of interest as well as mediating and moderating variables to address secondary aims. This briefly summarizes the primary outcome measures, describes the dependent measures to address the primary study aims and summarizes all measures, collection mode and timing. **All data will be collected at baseline, monthly and when completed – at 6 months** to approximate the effect of the PaM or EUC on the groups separately and in unison. All participants at both the PaM and EUC sites will receive all measures. The primary measures against which the study is powered lie with the PWD and are **weight change and change in dysfunctional behavior**.

1. Person with Dementia measures:

Demographics collected only at baseline:

- Functional Assessment Staging Scale – level of independence in physical activities
- Mini-Mental Status Examination – rates level of dementia
- Characteristics – age, race/ethnicity, primary diagnosis/ health problems with focus on swallowing problems and possible dysphagia

Outcomes collected baseline, monthly and completion

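### One randomised unit per arm: the PaM–EUC comparison is the comparison of two pooled Sites, so randomisation supports no efficacy test and the efficacy and power wording must be qualified

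*Combined protocol and SAP*

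**What the plan says.** Section C (Study Overview) builds two groupings intended to balance size and race. The ARK plus one Respite Care Charleston centre is the first: "Together they will be one Site for treatment condition and analysis". The other four Respite Care Charleston centres form the second. Then: "These two Sites will then be randomized to PaM and EUC". The split of 2 PaM and 4 EUC sites in Section A (Research design) matches these groupings.

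The claims made for this design are:

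- Section C: "a cluster design will be used to determine the efficacy of the Partners at Meals (PaM) train-the-trainer program".
- Section A, Aim 1: "To use a repeated-measures, randomized control design to assess the relative efficacy of Partners at Meals (PaM") against EUC.
- Section D (Measures, data sources and collection): "The primary measures against which the study is powered lie with the PWD and are" change in weight and in mealtime behaviour.

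On the unit of analysis, Section A says "The primary unit of analysis is the PWD and CG: 60 PWDs, 60 CGs will be enrolled". The one limitation admitted is baseline imbalance in cognitive and behavioural level: "since this is cluster design, we cannot assure an equal balance".

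No alpha, power, effect size, SD, intraclass correlation (ICC) or analysis model is given for Aims 1–2. The only statistical analysis text, in Section D, belongs to the online provider survey.

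The site descriptions also disagree:

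- **Number of sites.** Section A has "A randomized cluster-design trial will be conducted in two large RCCs with six sites", and Section C also adds up to six. Section D (Recruitment) and Section E.1.a (Sample) say five.
- **Randomised unit.** Section C randomises pooled Sites. Section A speaks of randomising RCCs, and Section E.2.a of randomising sites.

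**The concern.** With a single randomised unit in each arm, treatment and Site are the same variable. Anything that makes six-month change differ between the two groupings (staffing, meals served, case mix not captured by the baseline scales, or organisation, since The ARK lies wholly in one arm) enters the estimate as if it were a PaM effect. The randomised units contain no replication from which to judge how large such a difference might be. Recruiting more PWDs sharpens the estimate of the Site difference but does not separate it from treatment.

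What is at stake is the conclusion on Aims 1 and 2. The trial can estimate a difference between two site groups. A statement that PaM was shown efficacious in a randomised comparison would claim more than the allocation can support.

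**Working it through.** **The plan's own figure.** The 60 PWDs cannot be reproduced, because no inputs are stated. For orientation only: 30 per arm, independent PWDs, two-sided 5% and 80% power give a detectable difference of (1.960 + 0.842) × √(2/30) = 0.72 SD.

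**What the allocation supports (no assumptions).**

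| Reading | Units | df (units − 2) | Allocations | Smallest randomisation p |
|---|---|---|---|---|
| Two pooled Sites (Section C) | 2 | 0 | 2 | 0.5 one-sided, 1.0 two-sided |
| Six RCCs individually, 2:4 | 6 | 4 | 15 | 1/15 = 0.067 |
| Five sites individually, 2:3 | 5 | 3 | 10 | 1/10 = 0.10 |

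No reading of the text reaches 0.05.

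**Illustration of size.** Everything here is assumed: 30 PWDs per arm, one change score each, six centres, and ICC of change 0.01/0.02/0.05/0.10.

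*PWDs treated as independent, one shared effect per pooled Site.* The within-arm variance estimates only (1 − ICC) of the total. The ratio of true to assumed variance is therefore 1 + n × ICC/(1 − ICC), with n PWDs per arm. For n = 30 this is 1.303/1.612/2.579/4.333. At ICC 0.10, the critical value 2.002 (58 df) becomes 2.002/√4.333 = 0.962, a type I error of 34%. The four values are about 8.5/12/22/34%, and simulation agrees. The ratio grows with n. The base for the 25% over-enrolment in Section D is not stated:

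- 24 per arm (60/1.25 = 48) gives 7.7/10.6/18.7/29.9%.
- About 38 per arm (60 × 1.25 = 75) gives 9.5/13.9/25.4/38.6%.

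*PWDs treated as independent, effects at the six centres.* Approximate variance in SD² of change: ICC × (Σw_A² + Σw_B²) + (1 − ICC) × (1/n_A + 1/n_B), where w is a centre's share of its arm.

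- Centres of 15, 15 against 7.5 × 4: Σw² terms are 0.5 + 0.25 = 0.75. At ICC 0.05 the variance is 0.0375 + 0.0633 = 0.1008 against 2/30 = 0.0667. The ratio is 1.51, and 1.96/√1.51 = 1.59 gives 11.1%.
- Centres of 22, 8 against 7.5 × 4: Σw² terms are 0.609 + 0.25 = 0.859, giving 12.1%.

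Formula and simulation together give about 6/7–8/11–12/17–19%. At ICC 0 the error is 5%.

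*Centre-mean t-test, six centres nested in arm (4 df; 3 df if there are five sites).* If effects act at the pooled Site, simulated type I error is about 5/7/12/20%. Replication of centres inside a Site does not measure a Site effect.

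**The case against.** The strongest reply is that the plan is not limited to a two-point comparison. Change scores remove stable level differences between Sites. Baseline FAST and MMSE allow adjustment for measured severity. Respite Care Charleston has centres in both arms. A model with centres nested in arm has 4 nominal df. The pooling is disclosed and has a stated reason. Naming PWD and CG as the unit of analysis does not mean that clustering will be ignored, so the inflation figures describe an analysis that no section prescribes. At ICC 0.01 to 0.02 with centre-level effects the inflation is modest, at 6–8%.

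Most of this stands, and it limits what may be said. The type I figures are conditional illustrations, not predictions. The alternatives help, but each needs an assumption that the randomisation does not supply, namely that no unmeasured effect on change acts at the pooled-Site level.

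Two stronger readings should be resisted. A reader might infer that 60 is miscalculated or the study underpowered; the documents give no inputs, so the power statement is unsupported, not shown to be wrong. A reader might also infer that the data can say nothing about PaM; they can yield an adjusted estimate between two site groups, interpretable under stated assumptions.

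**Conclusion.** The point holds. As Section C is written, PaM against EUC is completely aliased with Site: 0 df, two allocations, and no significance test that rests on the randomisation. This needs no assumed ICC. It also survives the alternative reading in which RCCs are randomised individually, where the smallest p is 0.067. No other section resolves it, and the admitted limitation concerns baseline balance, not lack of replication.

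The size of the error in a participant-level test depends on how strongly six-month change clusters, which the documents do not say. Under the stated assumptions it runs from slight (about 6%, centre-level effects, ICC 0.01) to severe (about 34%, pooled-Site effects, ICC 0.10). The wording on efficacy and power must be changed because it governs what the primary comparison may conclude.

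**What to change.** 1. In Section A (Research design and Aims 1–2) and Section C, describe the comparison as a non-confirmatory estimate between two site groups with one randomised unit per arm. In Section D (Measures), remove or qualify the statement that the study is powered.

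2. Report PWD-level differences in change, adjusted for the baseline outcome and baseline FAST and MMSE, with confidence intervals and no confirmatory efficacy claim. Add a sensitivity table over stated ICCs, for example 0.01 to 0.10. With s² the within-cluster residual variance, use:
   - centre-level effects: s² × [ICC/(1 − ICC) × (Σw_A² + Σw_B²) + 1/n_A + 1/n_B];
   - pooled-Site effects: s² × [2 × ICC/(1 − ICC) + 1/n_A + 1/n_B].

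   For example, with 30 per arm and ICC 0.10 the pooled-Site variance is s² × (0.2222 + 0.0667) = 0.2889 s². The 95% half-width is 1.96 × √0.2889 = 1.05 s. Since s² is 0.9 of the total variance, that is 1.00 SD, against 0.51 SD with no clustering. State beside the table that neither version removes the aliasing of Site with treatment.

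3. Reconcile three things: the number of sites (six in Sections A and C, five in Sections D and E.1.a); the randomised unit (pooled Sites in Section C, RCCs or sites in Sections A and E.2.a); and the unit of analysis (Site in Section C, PWD and CG in Section A).

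The cost is protocol wording and one table, with no new sites, participants or measures. The price is wider intervals and a weaker headline claim.

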Exploratory AIM 4 includes MUSC research project staff to implement the intervention to CG and PWDS residing at home and receiving respite services. The past 14 months brought limitations to in-person meeting and programming in respite care centers affecting clients, volunteers and staff alike. Electronic platforms including Telehealth are now more commonly used and will be used to eliminate some of those barriers by making the intervention available to those not ready or able to engage in respite center programming or attending respite centers currently experiencing fewer Volunteers prior to the COVID pandemic.

Recruitment, enrollment, participant eligibility South Carolina is largely a rural state with more than 1/3 of the population identifying themselves as African American (AA). We recruit in through partnerships with agencies that serve a diverse group of families often in Medically Underserved Areas of South Carolina. Councils on Aging, homehealths, community centers and formal and informal respite centers are all places where Project Staff has formed connections to support and recruit for this project through web-based newsletters, through take-home fliers, social media announcements and announcing the study at support groups.

AIMS 1, 2 and 3 Eligibility criteria for the Volunteers or Staff; be a regular volunteer or staff with current affiliation of working or have worked at RCC within the last 12 months and is amenable to commit to the 6 month length of the study; able to read and speak English, identify as comfortable in the teacher/coach role, and demonstrate ability to use televideo and photograph.

(All AIMS) Eligibility criteria for Persons with Dementia (PWD): aged ≥ 45 years; diagnosis of Alzheimer's disease or related dementia with mild to moderate stage as demonstrated by the Functional Assessment Staging Scale (FAST) of 4 or greater; absence of wasting disorders (e.g., HIV/AIDS, heart or renal failure or COPD, end-stage cancer) ; some supervision required or dysfunctional behavior present (e.g., redirection); not receiving enteral feeding or active treatment by a speech pathologist/therapist; not diagnosed with dysphagia as identified by CG or on RCC Intake Sheet. Those enrolled in or qualifying for hospice will not be included.

Eligibility criteria for Caregiver (CG): is not paid for services; provides 4 hours or more of care/day; assists with ADLs including meals; be able to speak and read English. This study will not enroll persons for whom English is not their primary language. We acknowledge this essentially excludes older Hispanic persons who are solely Spanish speaking. However, we plan to create a culturally tailored intervention for this population in future work. **AIM 4 Have or have access to computer with internet connection.**

Eligibility criteria for the Administrators/Managers: assumes an administrative position within the respite care site (PaM or EUC) who has worked with the organization for at least 3 months and plans to be in place for at least 9 more months.

The introduction of the study and consenting processes are described in Protection of Human Subjects.

Intervention (Partners at Meals):

(AIMS 1,2,3) The intervention (PaM) is a train-the-trainer process. This process is primarily overseen by the PI (TK); she will also be available for further training and consultation. The intervention begins with 3 initial sessions (each 90-minutes over 2 weeks) by the project staff trained in adult education and will occur in the intervention sites; and they will be repeated as needed in each RCC for all new volunteers. These **initial sessions** will include: an introduction to dementia and mealtime issues along with an evaluation; principles of adult education; and application and refinement of assessment and teaching skills with an evaluation. There will be **booster sessions** (90-minutes) after the first 6 weeks of training or as needed with project staff for all volunteers that include: challenges of implementation; application and refinement of

assessment and teaching skills. There will also be **observation of the volunteer or RCC staff-CG dyad** by the research project staff and RD (initially) and monthly by the project staff based on feedback from the RCC staff and CG through self-report questionnaires to include skills in assessment, mealtime issues and teaching. The plan will be reviewed during the first month, then monthly for the remainder of the 6-month intervention. Thus, the mealtime intervention is occurring, being evaluated and modified monthly based on the Place/ People/ Person of the Partners at Meals model.

Furthermore, under the supervision of project staff trained in adult education and the Registered Dietician (RD) the intervention delivered by the RCC volunteer or staff with the CG and PWD dyad will be **tailored to the PWD based on the initial assessment** of health conditions, nutrient intake (initially assessed a pre-post measure of food consumed at the RCC and at home), mealtime behaviors (EdFED XL), and perceived quality of life (QoL-AD) . Cultural factors will be ascertained via structured checklist that will allow further modification (e.g., avoidance of meat/fish products, food blessing rituals, eating of hot and cold foods with certain medical conditions). Perceived barriers, preferences, motivation and confidence in making change will be assessed by the Program Manager and Registered Dietitian (RD). Working with the Program Manager and the RD, the **RCC volunteer / staff or MUSC Project Staff (AIM 4) and CG will devise an initial plan of care for mealtimes**. An RD was chosen to be a part of the initial planning since the PWD who attend RCC programs may have co-morbidities as well as pharmacological therapy that may influence nutritional status and diet choice. Furthermore, the RD will use **assessment of nutrients and calories consumed based on digital pre-and post-photos (taken on the tablet) and food logs** that may warrant changes in the plan based on health changes or as other information is available, e.g. food insecurity.

The project staff **under the supervision of the PI (SQ) will be trained in the use of the tele-health component** in of the intervention; she will also be available for further training and consultation. Research Staff will then train the volunteers or RCC Staff and the volunteers or RCC Staff will train the CGs in an initial training and at the same times for booster sessions and observations as the mealtime plan (above). After instruction in the use of the tablet, the CG will make monthly photos and films of a breakfast, lunch and dinner using the tablet provided. These images will either be **sent via a password-protected HIPAA compliant system – Doxy.me** to be evaluated by the Volunteer or RCC Staff and the research staff. Alternatively, the tablet can be brought to the respite care site and images downloaded there. In partnership with the Volunteer or RCC Staff, and research staff, a plan will be made to either continue the activities in the current plan or to revise it. The **plan will be made initially after enrollment based on the tele-health images and the evaluation measures** (see next section), then **monthly** for the remainder of the 6-month intervention; the CG and Volunteer or RCC Staff will document their agreed upon plan with the goal of the CG becoming the ‘lead’ in the planning as time progresses to promote sustainability. During the intervention, the CG and Volunteer or RCC Staff or MUSC Project Staff (AIM 4) will **meet at least monthly** at the RCC in a private room or via DOXY.ME on the Tablet to review progress and resolve issues; the research project staff will attend the first two of these meetings to assure fidelity and facilitate the process (the RD may be consulted during these times or more frequently if needed). Thus, the mealtime intervention is occurring, being evaluated and modified monthly, based on the Place/ People/ Person of the Partners at Meals model. The RCC administrator/manager, staff and volunteers (and possibly the

RD) will have planned interactions with the Program Manager at one-month intervals to assess use of resources, skills and beliefs of RCC staff, satisfaction with the program and suggestions for improvement.

Administrators/Managers at the respite sites **will be interviewed** by the Program Manager every 3 months that the study is in place for satisfaction, willingness to continue the program after completion, any CG or volunteer dissatisfaction, and are asked for data regarding discharge or hospitalization of study participants to determine if the cause could be related to nutrition-related changes. The Administrator/Manager and the project staff will ‘check-in’ every month, or more often if needed, to report any urgent problems or issues that need a timely resolution. However, the Administrators/Managers will not be consented as they are not research subjects but engaged in research (Offsite form attached) and we will be collecting feasibility and evaluation/satisfaction information from them. **Formal evaluation** of the Volunteer or RCC Staff, CG and PWD will occur at baseline, monthly and at the end of enrollment (6 months) or earlier if the CG or PWD withdraw or are withdrawn (see next section).

If requested, a step-by-step outline of the sessions used to train the Volunteer or RCC Staff, and then the CG by the Volunteer or-RCC Staff as well as ‘booster’ sessions can be provided to the IRB, as well as weekly and monthly review activities accomplished by research team members.

Measures, data sources and collection. As noted in the Aims, there are key outcome measures of interest as well as mediating and moderating variables to address secondary aims. This briefly summarizes the primary outcome measures, describes the dependent measures to address the primary study aims and summarizes all measures, collection mode and timing. **All data will be collected at baseline, monthly and when completed – at 6 months** to approximate the effect of the PaM or EUC on the groups separately and in unison. All participants at both the PaM and EUC sites will receive all measures. The primary measures against which the study is powered lie with the PWD and are **weight change and change in dysfunctional behavior**.

1. Person with Dementia measures:

Demographics collected only at baseline:

- Functional Assessment Staging Scale – level of independence in physical activities
- Mini-Mental Status Examination – rates level of dementia
- Characteristics – age, race/ethnicity, primary diagnosis/ health problems with focus on swallowing problems and possible dysphagia

Outcomes collected baseline, monthly and completion

- Body weight and caloric intake – weight before meal in street clothing less outer garments; intake measured by images taken with tablet pre- and post-meals at pre-arranged times
- Edinburgh Feeding in Dementia Scale (EdFED XL with added questions) – 24-item scale for dysfunctional meal-related behaviors (images from the tablet may assist in validating behaviors in question)
- Quality of Life in Alzheimer’s Disease (QOL-AD) – 13 item instrument used in person with MMSE as low as 4

2. Caregiver measures:

Demographics collected only at baseline

- Age, race/ethnicity, employment, relation to PWD, living arrangement, hours/day caring for PWD

Outcomes collected baseline, monthly and completion

- Center for Epidemiological Studies – Depression Scale (CES-D) – widely used in CG studies
- Zarit 12-item Burden Scale – rated 0 – 4, used in prior CG studies
- European Quality of Life (Euro-QL) – measures health-related quality of life
- Self-efficacy for Change – based on CP3 Model (developed in pilot work)

3. Volunteer or RCC Staff measures (AIMS 1,2 and 3):

Demographics collected only at baseline

- Age, race/ethnicity, preparation for volunteer role including coursework or classes or personal experience as CG, frequency of attendance, years in role

Outcomes

- Self-efficacy for Change – based on CP3 Model instrument (developed in pilot work)
- Performance measures – self-report of fidelity to treatment, carry out or change mealtime plan, address questions, training issues, progress and participation (developed in pilot work)

4. RCC Administrator/Managers measures

Demographics collected only at baseline

- Age, education, training, years in role, roles and responsibilities, role as CG

Outcomes

- Overall satisfaction of staff and CGs
- Satisfaction with implementation issues, satisfaction with program, willingness to continue
- Discharge status of any PWDs in study – to institutional care, hospitalized related to nutrition-related problems

Online Global Survey of RCC providers

An online global survey of RCC providers will be conducted using a researcher developed survey instrument. The survey will explore RCC telehealth/video conferencing capabilities, their use pre and post the onset of the COVID-19 pandemic, and RCC provider attitudes and opinions towards communicating and delivering individualized and in-the home educational support services to caregivers and their families with these types of technologies.

The survey itself will be conducted via an online REDCap survey link that will be widely and electronically disseminated through local, state, national and international network of RCC provider agencies and member associations – who will in turn share the link and opportunity to participate in the survey with their members on their listserves and organizational websites. No PHI will be collected, a waiver of HIPAA authorization and consent will be utilized, as written consent is deemed impractical for a study of this design. Survey instructions will however be devised in accordance with Federal Regulations and MUSC IRB policy: - so, as to include information about the study, its purpose, the demands, risks, and a statement that by submitting their responses that the individual is voluntarily agreeing to participate in the research study. We are aiming to sample at least 120 participants, globally. As no identifiable PHI will be collected,

the risks associated with this participation in this portion of the study are considered minimal. Study compensation will not be provided for survey participation.

Eligibility criteria includes:

- aged 18 years and older;
- male and female employees at RCCs;
- ability to read and understand English; and,
- must have internet access.

Statistical analyses:

Responses to all items are not required to complete the survey. All responses will be evaluated with descriptive analyses under the intention-to-treat principal (ITT). Descriptive analyses will include frequency tables for categorical variables and mean, standard deviation, minimum, 1st quartile, median, 3rd quartile, and maximum for continuous variables. Data will be stratified by demographic variables. Additional analyses will evaluate the association among survey elements using appropriate statistical techniques based on the nature of the data and the research question(s). Categorical variables will be compared with other categorical variables using the chi-square or Fisher's Exact test and with continuous variables using ANOVA or a non-parametric alternative. Associations between pairs of continuous variables will be assessed using the Pearson or Spearman Correlation Coefficient. Finally, generalized linear models may be used for exploratory statistical modeling of outcomes of interest from this survey. Survey results will be shared with member associations and organizations, who will in turn share them with their members, ie. the survey respondents.

